Context: Bronchopulmonary dysplasia (BPD), or chronic lung disease of prematurity, is most commonly defined as oxygen dependence at 36 weeks postmenstrual age (PMA). BPD affects nearly half of surviving extremely preterm (<28 weeks gestational age) infants, and the incidence of BPD has increased over time. Infants with BPD face more than doubled odds of death after 36 weeks PMA or disability at 5 years compared to preterms without BPD. BPD is associated with abnormal lung function throughout childhood and significantly increases health care costs. Cognitive and respiratory outcomes are closely linked throughout the life course; thus, optimal long-term management of BPD during infancy may ultimately improve cognitive outcomes of this high-risk population.

Objectives: The primary objective is to compare the incidence of intermittent hypoxemia (IH) and total duration of hypoxia up to 6 months corrected age (CA) among infants with BPD randomized to higher versus lower oxygen saturation (SpO₂) target ranges. The secondary objective is to describe clinically relevant outcomes over the first 6 months in the two study groups.

Study Design: This is a randomized pilot clinical trial. Since the two SpO₂ target groups in the current trial represent the currently accepted range of clinical practice, neither group is labeled as “intervention” or “control.”

Setting/Participants: In collaboration with Hospital of the University of Pennsylvania (HUP) and its affiliate hospitals, potential participants will be enrolled from the Neonatal Intensive Care Units (NICUs) at The Children’s Hospital of Philadelphia (CHOP), Pennsylvania Hospital (PAH) and HUP. We will enroll up to 50 infants who were born <30 weeks and who remain on respiratory support at 34-44 weeks PMA (ie, have moderate or severe BPD). CA.

Study Interventions and Measures: Enrolled infants will be randomized to higher or lower SpO₂ target ranges (a target SpO₂ of >=96% or 90-94%). The study intervention will begin in the hospital and will continue at home until 6 months. We will utilize 2-second sampling and averaging times and measure IH longitudinally throughout the study period in all participants regardless of home oxygen use. We define IH as SpO₂<80% for ≥ 30 seconds. Primary outcomes are incidence of IH and total duration of hypoxemia up to 6 months CA. Specifically, these are measured as differences between the two groups in incidence of IH at 40 weeks PMA, 3 months CA, and 6 months CA and percent of recording time spent <80%, <85% and <90% SpO₂ over the study period. Secondary outcomes are growth, feeding development, health-related resource utilization and quality of life.

The study team will use novel technology to perform overnight continuous oximetry after discharge and until 6 months CA. These data will be transmitted wirelessly to the study team using a novel, compact and low-cost device, whenever relevant, supplemental oxygen will be titrated according to a study algorithm, in order to maintain study participants within the target SpO₂ ranges.

PROTOCOL SYNOPSIS

Study Title	The Bronchopulmonary Dysplasia Saturation TARgeting Pilot Trial
Funder	Thrasher Research Fund
Clinical Phase	Phase I (Pilot Study)
Study Rationale	Supplemental oxygen is a lifesaving therapy for premature infants and a common post-discharge treatment for BPD. There is limited evidence to guide the use of supplemental oxygen beyond the immediate newborn period. No controlled studies have described continuous oxygen saturation monitoring post-discharge for infants with established BPD or evaluated the safety and efficacy of reducing IH to improve outcomes of infants with established BPD.
Study Objective(s)	
Primary
 
 • To compare the incidence of IH ($\text{SpO}_2 < 80\%$ for ≥ 30 seconds) up to 6 months corrected age among infants with moderate or severe BPD randomized to higher versus lower SpO_2 target ranges. 
Secondary
 
 • To explore clinically relevant outcomes over the first 6 months in the two study groups.
Test Article(s)	
Preterm born infants who remain on respiratory support at 34-44 weeks PMA will be randomized to higher or lower oxygen saturation target ranges, which will be maintained until 6 months corrected age. Both of these target ranges are within the wider range commonly used in clinical practice.
 
 • For the lower target group our goal is to keep oxygen saturations between 90-94%. In hospital, inspired oxygen will be adjusted as needed to maintain target SpO_2. Monitoring will continue after discharge, and whenever children are discharged on supplemental oxygen, oxygen flow will be titrated monthly according to a standardized algorithm. • For the higher target group our goal is to keep oxygen saturations greater than or equal to 96%. In hospital, inspired oxygen will be adjusted as needed to maintain target SpO_2. Monitoring will continue after discharge, and whenever children are discharged on supplemental oxygen, oxygen flow will be titrated monthly according to a standardized algorithm.
Study Design	Randomized controlled pilot study.

Subject Population key criteria for Inclusion and Exclusion:	Inclusion Criteria 
 1. Pre-term male or female infants born at <30 0/7 weeks gestation 2. Current age 34 0/7 to 43 6/7 weeks postmenstrual age 3. Diagnosis of moderate or severe Bronchopulmonary Dysplasia based on the NIH consensus definition 4. Infant has never been discharged to home from the hospital Exclusion Criteria 
 1. Congenital anomaly or oncologic process likely to affect growth or respiratory status 2. Hemoglobinopathy or other blood disorder likely to affect oxygen saturations 3. Contraindication to nasal cannula use (for example, severe nasal septal breakdown) 4. Pulmonary hypertension requiring pharmacotherapy at the time of screening/enrollment 5. Tracheostomy 6. Intubated during entire eligibility period
Number Of Subjects	50 enrolled (42 evaluable) between CHOP, HUP, and PAH
Study Duration	Each subject's participation will last up to 8 months. The entire study is expected to last 3 years.
Study Phases	1) Baseline/Screening: screening for eligibility and obtaining consent
Screening	2) Phase 1: Inpatient
Study Treatment	3) Phase 2: Outpatient oxygen Saturation Monitoring (discharge to 6 months CA)
Follow-Up	4) Phase 3: Outcomes assessment at 3 and 6 Months CA
Efficacy Evaluations	
 1. Oximetry 2. Growth checks 3. Developmental assessment 4. Parent questionnaires
Safety Evaluations	
 1. Close supervision from study physician. 2. All adverse events will be recorded and reported in accordance with CHOP and all other regulatory requirements. All adverse events and near misses will be discussed during monthly study team meetings to continually evaluate participant safety and prevent future adverse events.
Statistical And Analytic Plan	The primary endpoints are the incidence of IH (SpO2 <80% for >=30 seconds) and total duration of hypoxia up to 6 months CA

among infants with BPD randomized to higher versus lower SpO₂ target ranges.

All secondary endpoints in this pilot study are exploratory and descriptive. The primary clinical outcome is growth in kilograms between 36 weeks PMA and 6 months CA. In addition, the study will also report:

- The change in other growth parameters - length (cm), weight for length, and head circumference (cm) - between 36 weeks PMA and 40 weeks PMA, 3 months CA, and 6 months CA.
- Differences between groups on a standardized feeding questionnaire at 3 and 6 months CA.
- Differences between groups in parent and child quality of life at 3 and 6 months CA.
- Differences between the groups in health care utilization at 3 and 6 months CA.
- Differences between the groups in development at 6 months CA.
- Safety, assessed as differences in growth, re-hospitalizations, and any safety events at 3 and 6 months CA.

DATA AND SAFETY MONITORING PLAN

[figure not shown]
Data will be managed and stored in a password-protected database using REDCap (Research Electronic Data Capture). Only study team members will have access to the REDCap database for data entry under the supervision of and after training by the PI. Hard copies of data collection instruments will be stored in a locked cabinet in the PI's locked office. Participants will be assigned a unique identifier that contains no protected health information (PHI). PHI will be coded as identifiable information in REDCap using REDCap's built-in security features. Access to the identifiers of the coded data will be controlled by the PI and only study team members will have access to the electronic and paper data.

The PI will be responsible for monitoring the data and safety of all participants. All study procedures will receive IRB approval prior to recruitment or enrollment of participants. In addition to the data management procedures outlined above, the PI will hold monthly study team meetings to evaluate the safety and progress of all research procedures. Standard procedures for all data collection methods will be reviewed at the start and periodically throughout the study. Data checks for errors will be performed prior to analysis. Adverse events and serious adverse events will be reported to the

TABLE 1: SCHEDULE OF STUDY PROCEDURES

Study Activity	Recruitment Phase & Screening	Enrollment Phase	Study Timeframe					
			Baseline 34-44 (weeks)	Discharge	Weekly after discharge	Monthly after discharge	3 Months CA	6 Months CA
Pre-Enrollment Pool EPIC-CHOP/PENN/PAH	X							
Medical Record Review	X							
Conduct Eligibility Screen	X							
Approach Families (Beginning 34weeks, PMA)		X						
Parental Consent			X					
Participant Randomization			X					
Weight, length, and head circumference are measured			X				X	X
Placement of SPO2 study monitors/ training with families					Continuous over 6 months			
Feeding questionnaire and diary							X	X
Data from monitor are reviewed by study team and family is contacted if needed					Weekly data transfers to CHOP			
Feeding Questionnaire**							X	X
ITQOL-SF47 (Parent/Child quality of life) **							X	X
Health care utilization data is collected							X	X
Bayley Scales of Infant Development Screener								X
Participant Compensation. Payments issued monthly(\$50/visit; up to 6 visits)						X		

Adverse Event/Serious Adverse Event Assessment			X	X	X		X	X
--	--	--	---	---	---	--	---	---

FIGURE 1: SCHEMATIC OF STUDY PROCEDURES

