3.2 Allocation to Treatment Groups and Blinding

Infants will be randomized to higher or lower oxygen saturation (SpO₂) target ranges. The randomization sequence will be determined in advance, stratified by gestational age (<27 and 27-29 6/7 weeks at birth) and severity of BPD (moderate or severe, see Table 3 below) and balanced in random blocks of 2 or 4 patients. Allocation will be concealed in sequentially numbered opaque envelopes. The envelope with the lowest number will be opened by study staff. This plan for allocation concealment and stratification by key biologic variables will protect the scientific rigor of the study. After randomization, study group assignments will not be blinded. Multiples will be randomized separately. The two target SpO₂ ranges in the current trial represent the middle and upper range of the currently accepted range of clinical practice in our center.

Table 3: Screening Definition of BPD

Level of respiratory support at 36 weeks PMA	Eligibility
Room Air	Not Eligible (No or Mild BPD)
<2 L nasal cannula and <30% oxygen*	Eligible (Moderate BPD)
<2 L nasal cannula and >=30% oxygen**	Eligible (Severe BPD)
>=2 L nasal cannula or any positive pressure	Eligible (Severe BPD)

* <30% but receiving supplemental oxygen (22-29%) for at least 12 hours per day
** >=30% for 12 hours or more per day

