3.3 Study Duration, Enrollment and Number of Sites

3.3.1 Duration of Study Participation

The study duration per subject will be up to 8 months, not including the screening and consent procedures. The baseline phase will last from the time of hospitalization until discharge, the

treatment phase and follow-up phase will take place during the time between discharge and the 6 month corrected age follow-up appointment.

Many of the children eligible for the study will be followed by the CHOP Chronic Lung Disease Program, which has both inpatient and outpatient components. In addition, all children will be eligible for routine care in the CHOP Neonatal Follow-up Program (NFP). It is anticipated that most outcomes assessments will be performed during routine pulmonary or NFP follow-up appointments. Growth parameters between 36 weeks PMA and 40 weeks PMA, 3 months CA, and 6 months CA will take place during scheduled follow-up appointments. Questionnaires will be collected at 3 and 6 months CA. All questionnaires will take approximately 15-30 minutes to complete.

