5.2.2 Efficacy Evaluations: Clinical

In this pilot study, physiologic (oximetry) data are the primary outcomes. All clinical outcomes/assessments of efficacy are exploratory and descriptive. Methods and timing of measures that will be used to assess efficacy are:

Primary Clinical Outcome:

Growth in kilograms between 36 weeks PMA and 6 months CA as well as other growth parameters.

- Change in Length (cm)
- Weight for length
- Head circumference (cm)

Secondary Clinical Outcomes:

- Feeding questionnaire: The questions that will be asked at 3 and 6 months are selected to assess feeding skills and estimate caloric intake. The questions are selected from longer questionnaires administered as part of the Millennium Birth Study, with permission from the author of the original study.(13)
- The ITQOL---SF47- Parent and child quality of life survey: The Infant Toddler Quality of Life Questionnaire™ (ITQOL) was developed for use in infants and toddlers at least 2 months of age up to 5 years. The Infant Toddler Quality of Life Questionnaire™ (ITQOL) adopts the World Health Organization's definition of health, as a state of complete physical, mental and social wellbeing and not merely the absence of disease. The survey was developed following a thorough review of the infant health literature and a review of developmental guidelines used by pediatricians. The ITQOL includes questions that assess the impact of health on both child and parent quality of life.
- Medical resource utilization recorded at 3 and 6 months corrected age: medications (including dose, route, frequency, and indication), doctor and emergency room visits, hospitalizations (whether or not in ICU, duration, and indication), therapies (type and frequency), and home equipment use. These data will be extracted from the EMR wherever possible and verified with the participant's parent(s).
- Development: Per standard of clinical care, the Bayley Scales of Infant Development- 3rd Edition Screening Test is administered to all children who attend the Neonatal Follow-up Program (NFP) at 6 months corrected age. (All children eligible for this study will be

followed at the NFP per standard of care) Results of this clinical evaluation will be recorded for the study.

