6.2 Secondary Endpoints

All secondary endpoints in this pilot study are essentially exploratory and descriptive. The primary clinical outcome is growth in kilograms between 36 weeks PMA and 6 months CA. In addition, the study will also report:

- The change in other growth parameters - length (cm), weight for length, and head circumference (cm) - between 36 weeks PMA and 40 weeks PMA, 3 months CA, and 6 months CA.
- Differences between groups on a standardized feeding questionnaire at 3 and 6 months CA.
- Differences between groups in parent and child quality of life at 3 and 6 months CA.
- Differences between the groups in health care utilization at 3 and 6 months CA.
- Differences between the groups in development at 6 months CA.
- Safety, assessed as differences in growth, re-hospitalizations, and any safety events at 3 and 6 months CA.

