9.1.2 Blinding

The plan for allocation concealment is described above in section 3.2. Given the nature of the intervention to be evaluated participants and research staff will not be blinded to group assignment.

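### The 6-month Bayley screener is compared between arms in an open trial, and nothing keeps the arm from its examiner, although the stated reason for not blinding does not reach that examiner

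*Combined protocol and SAP*

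**What the plan says.** Section 3.2 states: "After randomization, study group assignments will not be blinded". Section 9.1.2 gives the reason and names who is affected: "Given the nature of the intervention to be evaluated participants and research staff will not be blinded to group assignment". Neither section mentions outcome assessors, and no other section provides a masked assessor for any outcome.

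The synopsis and section 6.2 both list the developmental comparison: "Differences between the groups in development at 6 months CA". Section 5.2.2 says how the score arises. The Bayley "Screening Test is administered to all children who attend the Neonatal Follow-up Program (NFP) at 6 months corrected age" as part of standard care, and then "Results of this clinical evaluation will be recorded for the study". The study therefore uses a score produced by clinic staff.

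Length and head circumference are also reported by arm, as changes from 36 weeks PMA to 40 weeks PMA, 3 months and 6 months (section 6.2). On where outcomes are measured, section 3.3.1 says: "It is anticipated that most outcomes assessments will be performed during routine pulmonary or NFP follow-up appointments".

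Sections 5.2.2 and 6.2 call the clinical outcomes exploratory and descriptive. Section 6.3.2 nevertheless plans simple bivariate tests, with t-tests and chi-square tests as examples, for the exploratory outcomes left after the main models.

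**The concern.** The Bayley screener is administered and scored by a person, so an examiner who knows the arm can influence the result. Concealed envelopes and stratification (section 3.2) protect the trial up to randomization. They do nothing for outcomes measured months later.

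The reason in section 9.1.2 is sound for families, who live with the oxygen and the monitor, and for the study team, which makes the weaning decisions with a pediatric pulmonologist (section 3.1.3). It does not explain why a follow-up clinic examiner should be free to know the arm.

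At stake is how far a developmental difference seen in this pilot can be trusted. Section 6.3.2 expects the exploratory analyses to be of value in planning future studies, so a distorted estimate could carry forward even if nobody relies on its p-value.

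**Working it through.** The point rests mainly on reading the sections together. The arithmetic only illustrates scale.

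**1. Does the reason for not blinding cover the examiner?**
- Section 9.1.2 names participants and research staff.
- Section 5.2.2 places the Bayley in routine clinical care, with the study recording the result.
- Sections 3.1.3 and 4.3.1 give weekly oximetry review and weaning decisions to the study team.
- No section gives Neonatal Follow-up Program examiners a part in titration.

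The reason therefore does not extend to them. Their status is simply not stated.

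**2. Is masking workable at the 6-month visit?** Section 3.1.4 expects nearly all infants to be in room air by the end of the study, so few should be visibly on oxygen. Infants in either arm may be on oxygen, so a cannula does not by itself identify the arm. The examiner is already in place, so no assessor or visit is added.

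**3. Does the same hold for length and head circumference?** Only in part.
- The 36- and 40-week values are collected from the inpatient record (section 5.1.2), while alarm limits and electronic orders reflect the arm (section 4.2.1).
- The 3-month values may come from the follow-up program, the chronic lung disease program, the pulmonary clinic, the CTRC or a home visit (section 4.3.2).
- Growth is also taken from any clinical visit (section 5.1.4).

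Only the 6-month measurements made in the follow-up program are in the same position as the Bayley.

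**4. Illustration of scale.** The documents give no figure for examiner bias and no power statement for development, so there is no figure of the plan to reproduce.

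Input from the plan: 42 evaluable infants (section 6.4). Assumptions: a 21:21 split, a two-sided 5% level (neither level nor sidedness is stated), and a continuous score compared by t-test (the plan does not say how the screener is summarised).

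- SE of a difference = √(2/21) = 0.309 SD.
- Degrees of freedom = 42 − 2 = 40; critical t = 2.021.
- Noncentrality = assumed shift ÷ 0.309. Rejection probability comes from the noncentral t distribution, with no true difference between arms.

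| Assumed shift between arms (SD) | Noncentrality | Chance of a false difference |
|---|---|---|
| 0 | 0 | 5.0% |
| 0.1 | 0.32 | 6.2% |
| 0.2 | 0.65 | 9.7% |
| 0.3 | 0.97 | 15.8% |
| 0.4 | 1.30 | 24.4% |

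The true difference detectable with 80% power under the same assumptions is 0.886 SD (0.865 SD by normal approximation).

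**The case against.** **Silence is not disclosure.** A reader might infer that the plan uses examiners who know the arm. The documents do not say so. Section 9.1.2 speaks of research staff, and the Bayley examiners are described as giving standard care. The general sentence in section 3.2 leaves their status open. This objection stands: what is missing is a safeguard.

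**The direction of any bias is not settled.** A reader might infer that examiners would favour the higher arm. Section 2 does pose the question whether higher saturations improve clinical outcomes, section 6.4 assumes less weight gain in the lower arm, and section 9.4.2 says that more hypoxia at lower targets might affect growth and development. But sections 1.1 and 9.4.2 also say that high targets may bring toxicity with no neurologic gain, and section 3.1 labels neither arm as intervention or control. For development the expectation is mixed. This stands.

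**Growth is measured in many places.** A reader might extend the point to all length and head circumference data. The inpatient, pulmonary clinic, CTRC and home measurements could not readily be masked, so the wider claim fails.

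**The consequences are limited.** The primary outcomes are recorded by oximeter, the clinical outcomes are exploratory, no decision rule uses them, and section 6.3.2 itself warns of low power in the exploratory analyses. This stands and lowers the priority. It does not remove the point, because biased scoring distorts an estimate whether or not it is tested.

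**Withholding the arm could hinder care.** Section 3.1.4 gives the follow-up clinic a part in ongoing care, so keeping the arm out of clinic notes would have a drawback. This stands, and the fix avoids it.

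**Conclusion.** The concern holds in a narrow form. The trial is open, no assessor is masked, and the reason given for not blinding does not apply to the Neonatal Follow-up Program examiners who score the 6-month Bayley screener. The same applies, where feasible, to 6-month length and head circumference measured in that clinic. It does not apply to earlier growth measurements or to those made elsewhere.

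The size of any bias is unknown. The rise from 5% to about 10–24% for a shift of 0.2 to 0.4 SD is conditional on that shift. It also needs examiners who know the arm and lean one way across whole arms, and the documents establish neither. The conclusion about the text does not depend on these figures.

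This is a low-priority, inexpensive improvement to an exploratory outcome.

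**What to change.** In sections 9.1.2 and 5.2.2, leave titration unblinded and add the following:

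- The existing Neonatal Follow-up Program staff who administer the 6-month Bayley screener are not told the arm and do not consult the study assignment before scoring. Where feasible, the same applies to those who measure length and head circumference at that visit.
- Families are asked not to volunteer the arm to that examiner during testing.
- The examiner records whether the arm became known.

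The arm should not be withheld from notes or from staff who need it for care.

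The report should state that the inpatient 36- and 40-week measurements, and 3-month measurements made in the pulmonary clinic, the CTRC or at home, were not masked.

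Cost: protocol wording, a short instruction to clinic staff and one extra data item, with no new assessor or visit. The documents give no costs, so calling this cheap is a judgement. Masking will be partial, because parents may disclose the arm, a few infants may still be visibly on oxygen, and the arm may be visible in the record. The recorded unmasking rate would show whether masking is workable in a larger trial. If the sponsor judges it unworkable, unmasked assessment should be stated as a limitation of the developmental comparison.
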